Cover Page

Official title of the study: A Randomized Clinical Trial to Assess the Efficacy of Intrauterine Balloon Compared to Intrauterine Contraceptive Device Plus Foley Catheter in the Therapy for Uterine Adhesion After Hysteroscopic Adhesiolysis. Date: 12/01/2017

Clinical Trial Registration Number: NCT02867202

Study protocol

The problem to be investigated

Project title: A Randomized Clinical Trial to Assess the Efficacy of Intrauterine Balloon Compared to Intrauterine Contraceptive Device Plus Foley Catheter in the Therapy for Uterine Adhesion After Hysteroscopic Adhesiolysis.

Research problem: This is a RCT designed to compare the efficacy of heart-shaped intrauterine balloon and Intrauterine Contraceptive Device Plus Foley Catheter in the prevention of adhesion reformation after hysteroscopic adhesiolysis. Background: The prevalence of IUAs varies from 0.2% in patients who undergo an intrauterine device insertion to 66.7% in patients with miscarriage curettage before. (Schenker & Margalioth, 1982) Hysteroscopic technique remain an accurate diagnosis for presence, degree of adhesions during the last two decades. (Fernandez, Al-Najjar, Chauveaud-Lambling, Frydman, & Gervaise, 2006)Hysteroscopic adhesiolysis currently become a safe and effective management to restore normal uterine cavity, however, the high incidence rate of postoperative adhesion reformation is a main challenge and difficult to solve, especially in patients with severe IUAs, in whom the recurrence rate was

reported up to 62.5%. (Yu, Wong, Cheong, Xia, & Li, 2008)Various adjunctive treatments have been proposed in an attempt to reduce postoperative recurrence. Despite the many proposed solutions, no particular method has proven to be the optima measure in preventing adhesion formation. Thereby, we put forward a new approach which combine intrauterine contraceptive device (IUD) with Foley catheter in the prevention of postoperative adhesion reformation, and there is as yet no study to confirm its value.

The aims: The aim of our study was to evaluate the efficacy of IUD plus Foley catheter and intrauterine balloon after hysteroscopic adhesiolysis in patients with moderate to severe adhesion according to the American Fertility Society (AFS) classification of intrauterine adhesions.

(v) The hypothesis: IUD plus Foley catheter presented a greater improvement in adhesion score than heart-shaped balloon in a retrospective study

2. Methods of investigation:

Subjects: The patients were totally recruited from the 1st affiliated hospital of Wenzhou Medical University between August 2016 and December 2017.

Inclusion Criteria:

1) women aged 18 to 45 years.

2) patients had no history of hysteroscopic adhesiolysis.

3) agreed to have second-look hysteroscopy.

4) moderate to severe IUA (AFS score \geq 5) according to

American Fertility Society (AFS) scoring system.

5) written informed consent obtained.

Exclusion Criteria:

1) minimal adhesion (AFS score <5) and

2) previous hysteroscopic adhesiolysis.

3) Inability or refusal to provide informed consent

Design: Prospective, randomized, controlled trial.

Experimental procedure: The heart-shaped intrauterine balloon is designed to fit into the cavity of the uterus, and removed on the 7th day after surgery. And hysteroscopy was taken out again after two menstrual cycles to evaluate the uterine adhesions. Intrauterine Contraceptive Device Plus Foley Catheter are inserted into the uterine after a hysteroscopic adhesiolysis. Foley Catheter is removed after three days while IUD removed at the second hysteroscopy. Uterine adhesions were judged again at the second hysteroscopy. The presence of adhesion was confirmed and uterine anatomy had been assessed at first-look and second-look hysteroscopy.

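### Should second-look adhesions be scored by a masked assessor, given that the IUD is still in place at that visit?

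*Protocol*

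**What the plan says.** Protocol section 2, Experimental procedure, gives the two arms different device schedules. The heart-shaped balloon is "removed on the 7th day after surgery". In the comparison arm, "Foley Catheter is removed after three days while IUD removed at the second hysteroscopy".

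The outcome is taken at one visit: "And hysteroscopy was taken out again after two menstrual cycles to evaluate the uterine adhesions". The text continues "Uterine adhesions were judged again at the second hysteroscopy", and closes with "The presence of adhesion was confirmed and uterine anatomy had been assessed at first-look and second-look hysteroscopy".

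The design line calls the trial prospective, randomized and controlled. Neither document mentions blinding, masking or an independent assessor, says who scores, or says whether scoring comes before or after IUD removal.

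The Background describes the IUD combination as the team's own proposal ("we put forward a new approach which combine intrauterine contraceptive device (IUD) with Foley catheter"), and the hypothesis cites a favourable earlier result: "IUD plus Foley catheter presented a greater improvement in adhesion score than heart-shaped balloon in a retrospective study".

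SAP item 2 sizes the trial on adhesion recurrence, 46% with the balloon against 18% with IUD plus Foley. SAP item 3 compares reformation rates by chi-squared or Fisher's exact test, and the reduction in AFS score by the Mann-Whitney test.

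**The concern.** Three things coincide. The endpoint that sizes the trial is a visual judgement. Only one arm still has a device in the uterus at the visit where that judgement is made. The team has also recorded which arm it expects to do better. A scorer who sees or removes the IUD knows the arm and may call doubtful findings in its favour.

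Randomization does not protect against this, and no test in the SAP can undo it afterwards. The point is also narrower than a general request for blinding: surgeon and patient could stay unmasked and the scorer still be kept unaware of the arm. At stake is whether a significant difference in recurrence could come from scoring rather than from the devices.

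**Working it through.** **The plan's own figure.** SAP item 2 gives 53 per arm. The unpooled normal formula at two-sided 0.05 and 90% power gives (1.960 + 1.282)² × (0.46 × 0.54 + 0.18 × 0.82) / 0.28² = 53.07, which matches. With 20% drop-out, 106 / 0.8 = 132.5, against the stated 132. Masking the scorer would not alter either number.

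**What biased scoring could do (illustration only).** Assume no true difference, a true recurrence rate p in both arms, and a scorer who misses a share f of IUD-arm recurrences. The observed IUD-arm rate is then p × (1 − f). For example, 0.32 × (1 − 0.20) = 0.256, where 32% is the mean of 46% and 18%. The table gives the chance of a significant result favouring the IUD, by exact enumeration at two-sided 0.05. Each range covers 53 to 66 per arm.

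| True rate p | Test | f = 0 | f = 5% | f = 10% | f = 20% | f = 40% |
|---|---|---|---|---|---|---|
| 18% | Pearson | 2.4–2.5% | 3.3% | 4.3–4.4% | 7.1–7.8% | 17.7–21.1% |
| 18% | Fisher | 1.4–1.5% | 1.9–2.1% | 2.5–2.8% | 4.3–5.2% | 11.6–15.3% |
| 32% | Pearson | 2.5–2.6% | 3.9% | 5.6–5.9% | 11.2–12.4% | 33.6–39.0% |
| 32% | Fisher | 1.5–1.7% | 2.3–2.6% | 3.5–4.1% | 7.4–9.1% | 25.4–32.2% |
| 46% | Pearson | 2.3% | 4.0–4.2% | 6.7–7.2% | 16.0–18.3% | 51.7–60.3% |
| 46% | Fisher | 1.5% | 2.7–2.9% | 4.6–5.2% | 11.9–14.2% | 43.7–53.5% |

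The spread is wide, and the documents give no value of f. Mild miscalling barely matters; heavy miscalling would matter a great deal.

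**What masking would require.** While the IUD is in the cavity, any view of it, live or recorded, identifies the arm. A masked score in the IUD arm must therefore come after removal, and must be made by someone who neither removes the IUD nor watches. This has two consequences.

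1. A second hysteroscopist is needed. To avoid signalling the arm, that person must score in both arms. Recruitment ran "between August 2016 and December 2017", 17 calendar months. That is 132 / 17 = 7.8 second looks a month, or 106 / 17 = 6.2 if drop-out means no second look. Staffing is not stated.
2. The order becomes removal, then scoring, in one arm only, because balloon-arm women have no device to remove at that visit. Suppose removal disturbs a share g of IUD-arm recurrences so that they are not recorded. The observed rate is then p × (1 − g), the same expression as for miscalling and in the same direction. Masking exchanges f for g and helps only if g is smaller than f. The documents give neither.

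**How much a change could still reach.** Assume even accrual from 1 August 2016 to 1 or 31 December 2017, and 42 to 70 days for two menstrual cycles. The document date, 12/01/2017, can be read two ways.

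| Reading of the date | Second looks still ahead, of 132 | Same shares applied to 106 |
|---|---|---|
| 12 January 2017 | 99–108 (75–82%) | 79–87 |
| 1 December 2017 | 11–26 (9–19%) | 9–21 |

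If the past tense of the Protocol is taken literally, none remain. Take p = 32% and f = 20%, and suppose masked scoring removes all miscalling in the women it reaches. If it reaches 79% of them (56 days, accrual to 31 December, January reading), the Pearson figure falls to about 3.7%. If it reaches 17% (the same case, December reading), the figure stays at 9.0–9.7%.

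**The case for a change.** The strongest reply is that the silence is itself the defect: a reader cannot tell whether the endpoint that sized the trial was scored by someone who knew the arm. The remedy also seems cheap, since the balloon is already out, the IUD comes out at that visit anyway, and the visit and sample size stay as they are. If every second look is done, disclosure remains possible.

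Part of this stands. The schedule does expose the arm, the team's expectation is on record, and the report should say who scored and name unmasked scoring as a limitation if that is what happened.

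The claim of low cost does not stand. It assumes a second scorer whom the documents do not provide, and it leaves out the order effect in the IUD arm. Showing recurrence separately for masked and unmasked second looks would not settle the matter either. If masking starts part-way through, that split also compares earlier with later patients and cannot isolate the effect of masking. Nor does it help to count how many reclassified women would overturn a significant result, because that count would be the same under perfect masking.

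**Conclusion.** The observation is accurate: no masking is described, and the scorer can identify the arm unless scoring is separated from IUD removal. The documents do not show that scoring was unmasked or that any bias occurred.

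No change to the plan follows. The only step that could reduce the bias needs an additional assessor and commits the trial to an order of removal and scoring that carries its own possible bias in the same direction. That is a fair trade-off for a small single-hospital trial to leave alone. The rest of the remedy is missing detail that the trial report can supply, and supplying it would alter no analysis or result.

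The range is wide. Across true recurrence of 18% to 46% and assumed miscalling of 5% to 20%, the chance of a false Pearson result favouring the IUD runs from 3.3% to 18.3%, against about 2.5% with no miscalling. At 40% miscalling it would be 17.7% to 60.3%. These figures rest on assumed miscalling shares and say nothing about what happened in this trial. A reader should weigh the recurrence result as one that may have been scored with knowledge of the arm.

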Cover Page

Official title of the study: A Randomized Clinical Trial to Assess the Efficacy of Intrauterine Balloon Compared to Intrauterine Contraceptive Device Plus Foley Catheter in the Therapy for Uterine Adhesion After Hysteroscopic Adhesiolysis.

Date: 12/01/2017

Statistical Analysis Plan

- 1. Measurements used: This study was taken out to compare two mechanical devices (intrauterine balloon and Intrauterine Contraceptive Device Plus Foley Catheter) in the therapy for intrauterine adhesions after hysteroscopic adhesiolysis. The efficacy in the prevention of adhesion reformation after hysteroscopic adhesiolysis for Asherman syndrome was compared between the groups.
- 2. Sample size calculation: Assuming that the adhesion recurrence rate was 46% in patients with intrauterine heart-shaped balloon insertion and in the group receiving intrauterine contraceptive device (IUD) plus Foley catheter was 18%, and accepting a type 1 error (α) of 0.05, and a type 2 error (β) of 0.10, the number of subjects required was 53 in each arm. After assuming the drop-out rate of 20%, the total number of subjects required was 132.
- 3. Statistical methods: Data analysis was performed with SPSS

version 22.0 (SPSS, Inc., Chicago, IL, USA), using two-sided test, and a p value < 0.05 was considered statistically significant. The continuous variables were analyzed by the Student's t test. The rate of reformation adhesions were described as percentages and were evaluated using chi-squared (χ 2) test or Fisher's exact test. The Mann-Whitney test was used to compare the reduction of AFS score between the groups.

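### Does leaving the choice between chi-squared and Fisher's exact test open undermine the 90% power claimed for 53 women per arm?

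*SAP*

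**What the plan says.** Section 2 of the SAP (Sample size calculation) assumes that "the adhesion recurrence rate was 46% in patients with intrauterine heart-shaped balloon insertion" and that recurrence "in the group receiving intrauterine contraceptive device (IUD) plus Foley catheter was 18" per cent. It sets the error rates by "accepting a type 1 error (α) of 0.05" and "a type 2 error (β) of 0.10", and concludes that "the number of subjects required was 53 in each arm". With 20% drop-out it adds that "the total number of subjects required was 132". It names no formula, software or test for this calculation.

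Section 3 (Statistical methods) sets the decision rule: "using two-sided test, and a p value < 0.05 was considered statistically significant". For recurrence it says "The rate of reformation adhesions were described as percentages and were evaluated using chi-squared", with Fisher's exact test as the alternative. It does not say what decides between the two, or whether the chi-squared statistic carries a continuity correction.

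**The concern.** A power figure belongs to a particular test, and here the calculation and the analysis are not visibly linked. The closest match to 53 is a formula with unpooled variance, rounded down, whereas Pearson's chi-squared uses the pooled variance and needs a few more women. Fisher's test is conservative and needs about ten more per arm. On that reading neither named test delivers the stated 90%, and with Fisher the chance of missing a true difference of the planned size would be about 16% instead of 10%.

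Two further points seemed to add to this. The drop-out inflation is also rounded down. And an unexplained choice between two tests looks like an opening to pick the p value once the data are in, which, if real, would threaten the validity of the result and not only its power.

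**Working it through.** **Inputs (SAP sections 2 and 3).** Recurrence p1 = 0.46 (balloon) and p2 = 0.18 (IUD plus Foley); difference 0.28; two-sided alpha 0.05; power 0.90; equal arms, implied by the single per-arm figure; drop-out 20%.

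**1. Reproducing 53.** Unpooled formula:

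n = (1.960 + 1.282)² × [p1(1 − p1) + p2(1 − p2)] / (p1 − p2)²

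The variance sum is 0.46 × 0.54 + 0.18 × 0.82 = 0.2484 + 0.1476 = 0.3960, and 0.28² = 0.0784. With unrounded normal quantiles, n = 53.07. By this formula, power at 53 is 89.96%. The plan's figure is reproduced, although the formula is inferred. A one-sided pooled formula with continuity correction also gives 53, but it conflicts with the SAP's two-sided testing.

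**2. Pooled formula, which matches Pearson's test.** The mean rate is 0.32, and 2 × 0.32 × 0.68 = 0.4352.

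n = [1.960 × √0.4352 + 1.282 × √0.3960]² / 0.0784 = 56.2, so 57 per arm.

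**3. Exact power.** This sums the two binomial distributions over every possible table and counts those with p < 0.05:

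| Per arm | Pearson | Yates | Fisher |
|---|---|---|---|
| 53 | 88.9% | 83.9% | 83.9% |
| 54 | 89.2% | 84.9% | 84.9% |
| 56 | 90.4% | 86.6% | 86.6% |
| 63 | 93.2% | 90.0% | 90.5% |
| 66 | 94.3% | 91.8% | 91.8% |

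Pearson first reaches 90% at 56 per arm and Fisher at 63. Rounding 53.07 up to 54 would have gained 0.3 points with Pearson and 1.0 with Fisher, so the rounding explains little of either gap. The last row is the case in which nobody drops out.

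**4. Would Fisher be called for?** The smallest expected cell at the planned rates is 53 × 0.32 = 17. For it to fall below 5 with 53 per arm, there would have to be fewer than 10 recurrences in total. The planned rates predict 53 × 0.46 + 53 × 0.18 = 33.9.

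**5. Can the choice of test be exploited?** All tables with 53 per arm were classified by both tests. None is significant by Fisher and not by Pearson; 98 are significant by Pearson and not by Fisher. Reporting whichever test is significant is therefore identical to using Pearson throughout. Pearson's exact type 1 error lies between 4.6% and 5.3% at common recurrence rates of 18%, 25%, 32%, 40% and 46% (5.2% at 32%).

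**6. Drop-out.** 2 × 53 / 0.80 = 132.5, stated as 132, which is an even 66 per arm. Then 132 × 0.80 = 105.6 evaluable women against 106. Even 52 per arm gives 88.2% with Pearson.

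**The case for a change.** The best case for a change is that it would be cheap and would remove a real ambiguity. At the planned rates with 53 per arm, the two tests disagree on significance in about 5% of trials; with no true difference (32% in both arms) they disagree in 2.2%. A reader cannot tell from the SAP which p value is the confirmatory one. An unqualified reference to chi-squared does not exclude the Yates correction, which is as costly as Fisher. One or two sentences would settle it without adding a patient.

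The disagreement figures are right, and so is the observation that no selection rule is written down. But the disagreements all run one way, with Pearson significant and Fisher not. An analyst who used Fisher without need would lose about five points of power (88.9 − 83.9) and would be conservative: at 32% in both arms Fisher rejects in 3.1% of trials against 5.2% for Pearson. That is a loss of sensitivity, with no threat to validity. Naming the two tests together is also common shorthand for chi-squared unless expected counts are small, and that reading leads to Pearson here.

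**Conclusion.** The concern does not justify a change. The stated 53 per arm is sound under a standard two-sided formula, and the test that would ordinarily be used has exact power of 88.9%, 1.1 points below target. That gap is small beside the uncertainty in the assumed 46% and 18%. The 84% figure is correct but conditional on Fisher or a Yates correction deciding the result, and nothing at the planned rates calls for Fisher. The freedom to choose adds no false-positive risk beyond that of Pearson alone. The drop-out rounding costs less than half a woman.

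What is left is an unwritten rule that analysts would fill in the usual way, with a sound result. Writing it down would alter neither the number of women nor the likely analysis. The conclusion rests on roughly equal arms of about 53 evaluable women, recurrence near the planned rates, and the uncorrected chi-squared test when expected counts are adequate.

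### Recurrence is tested only by an unadjusted comparison; if first-look AFS score is prognostic, pre-specified adjustment for it would give a small gain in precision and protect against chance imbalance (optional)

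*SAP*

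**What the plan says.** SAP section 3 gives one analysis for recurrence: "The rate of reformation adhesions were described as percentages and were evaluated using chi-squared" or Fisher's exact test, two-sided at 5%. It names no covariate, regression model or stratified test for this outcome. The same section compares the reduction in AFS score by a Mann-Whitney test. That test uses the first-look score, but for a different outcome, so it does not adjust the recurrence comparison.

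The protocol's background describes reformation as a difficulty "especially in patients with severe IUAs, in whom the recurrence rate was" "reported up to 62.5"%. The inclusion criteria admit "moderate to severe IUA (AFS score" of 5 or more), and the exclusion criteria rule out "minimal adhesion (AFS score <5"). Under Experimental procedure, "The presence of adhesion was confirmed and uterine anatomy had been assessed at first-look and second-look hysteroscopy". A first-look score should therefore exist for every randomised woman.

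On design, the protocol says only "Prospective, randomized, controlled trial". It mentions no stratification by severity.

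**The concern.** On the protocol's own account, severity is a plausible predictor of recurrence, and entry spans moderate to severe disease. If the score does predict recurrence, the crude comparison gives something up in two ways. On average it has slightly less power than an analysis that uses the score. In a particular trial of about 106 evaluable women, a chance difference in severity between arms moves the crude estimate up or down, and the plan has no analysis with which to answer a reader who notices it. Adding adjustment once the imbalance is visible would be post hoc, whereas naming it beforehand costs little.

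**Working it through.** **The plan's own figure.** Inputs from SAP section 2: 46% and 18%, α = 0.05 two-sided (section 3), β = 0.10. With unpooled variance, n per arm = (1.960 + 1.282)² × (0.46×0.54 + 0.18×0.82) / 0.28² = 53.07, matching the stated 53. For dropout, 106 / 0.8 = 132.5, matching 132 apart from rounding. Exact power at 53 per arm is 88.9% for the uncorrected chi-squared test and 83.9% for Fisher's test. The chi-squared test, the more favourable of the two, is the benchmark below.

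**Assumptions not in the documents.** AFS scores run from 5 to 12 and are evenly spread; log-odds of recurrence are linear in the score; randomisation is unstratified. The documents give no maximum score, no severe share, no moderate/severe cut-off and no recurrence rate in moderate disease. Intercepts were solved so that the arm rates stay at 46% and 18% (32% in both under the null).

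**Average performance**, 40,000 simulated trials per cell. The adjusted analysis is a logistic regression on arm and score with a likelihood-ratio test (LRT) for arm. The odds ratio from score 5 to score 12 is exp(7 × slope).

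| Slope per point | Odds ratio, 12 v 5 | Crude power | Adjusted power | Change, points | Change with test size matched | Variance, adjusted/crude |
|---|---|---|---|---|---|---|
| 0 | 1.0 | 88.8% | 88.7% | -0.1 | -0.4 | 1.01 |
| 0.1 | 2.0 | 88.7% | 88.9% | +0.2 | 0.0 | 1.00 |
| 0.2 | 4.1 | 88.9% | 90.0% | +1.1 | +1.0 | 0.97 |
| 0.3 | 8.2 | 88.7% | 91.0% | +2.3 | +2.1 | 0.92 |
| 0.4 | 16.4 | 89.1% | 92.9% | +3.8 | +3.7 | 0.87 |

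The size-matched column comes from a separate run in which the LRT was held to the chi-squared test's simulated null rejection rate. The variance ratio of 0.87 at slope 0.4 corresponds to 106/0.87 - 106, or about 16 extra women. With scores skewed low or high, the largest gain ranges from 2.7 to 3.8 points. If risk instead steps up at an assumed score of 9, with odds ratios of 2 to 5, the linear-score analysis gains 0.2 to 2.5 points. The mean standardised difference stays at 27.9 to 28.1 points although the model is then wrong in form.

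**Error rates.** Null rejection is 5.0 to 5.6% for the LRT and 4.6 to 5.3% (exact) for the chi-squared test. Coverage of the 95% interval for the standardised risk difference is 94.4 to 94.9% with an influence-function standard error. With a percentile bootstrap it is 93.5 to 94.6%, and null rejection is 5.7 to 6.1%.

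**Chance imbalance.** The SD of a score evenly spread over 5 to 12 is √(63/12) = 2.29. The SE of the difference in arm means is 2.29 × √(2/53) = 0.445. A gap of at least 0.6 in a given direction is 0.6/0.445 = 1.35 SE, with probability about 9%. At slope 0.3 the crude difference then moves by roughly 0.3 × 0.6 × (0.2484 + 0.1476)/2 = 0.036, or 3 to 4 points around 28. Simulated power, given a gap of 0.5 to 0.7:

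| Slope | Balloon arm lower: crude / adjusted | Balloon arm higher: crude / adjusted |
|---|---|---|
| 0.1 | 85.9% / 88.8% | 91.3% / 88.9% |
| 0.2 | 82.9% / 89.3% | 93.7% / 89.9% |
| 0.3 | 81.0% / 91.2% | 95.3% / 90.9% |
| 0.4 | 78.8% / 92.8% | 96.8% / 93.0% |

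At slope 0.3 the crude difference averages about 24 to 25 points in the first case and 31 in the second. The adjusted estimate stays near 28 in both.

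**The case against.** The strongest reply is that nothing is broken. A chi-squared test on two proportions matches the contrast used for sizing, and randomisation with a 5% level already allows for chance imbalance. That stands, and it is why this is an optional improvement. A reader might infer that the crude test is biased, or that the trial is underpowered without adjustment. Neither follows: the crude difference averages 28 points over repeated trials, and its power is 89% whatever the slope.

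A second reply is that the size of the benefit has no numerical basis in the documents. This also stands. A reader might take the 62.5% figure as proof that severity is prognostic here. It is a single upper figure for severe disease with no rate for moderate disease beside it, so it makes prognosis plausible but gives no strength. The larger gains need strong association: an 8-fold odds difference across the assumed range at slope 0.3 and 16-fold at 0.4. At slope 0.1 the gain is nil.

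Third, the imbalance figures are conditional on an unlucky draw with about a 9% chance in each direction (the 9% is for gaps of 0.6 or more, the powers for gaps of 0.5 to 0.7), and in the mirror case adjustment lowers power. That is correct, so adjustment should not be presented as a gain in every trial.

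Fourth, the open choice between chi-squared and Fisher is worth about 5 points of power (88.9% versus 83.9%), more than the largest average gain here. That is true and deserves fixing as well, but it does not remove this point.

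Finally, the change may come too late. Recruitment ran "between August 2016 and December 2017". The SAP date, 12/01/2017, can be read as January or December, and the SAP is written in the past tense. The documents do not show whether outcomes by arm had been seen.

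**Conclusion.** The point holds as an optional improvement. The planned test is valid. If first-look AFS score is prognostic, adjusting for it gives a small average gain: about 0 to 4 points of power and about 0 to 13% less variance for assumed linear slopes of 0.1 to 0.4 per point. It also keeps the estimate near 28 points when chance makes the arms differ in severity, in either direction. If the score is not prognostic, the cost is about 0 to 0.4 points of power. These sizes rest on an assumed 5 to 12 range, an assumed score distribution, assumed prognostic strength and unstratified randomisation. Confidence is medium, because the documents supply no rates by severity.

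**What to change.** Before outcomes are examined by arm, amend SAP section 3 as follows.

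- Name one primary recurrence analysis: logistic regression on arm and first-look AFS score as a linear term. No moderate/severe cut-off is needed. Take the p value from the likelihood-ratio test for arm.
- Report the standardised risk difference, which keeps the 46% versus 18% contrast used for sizing, with a 95% confidence interval from an influence-function (robust or delta-method) standard error. Do not use a percentile bootstrap, which under-covers slightly here.
- Keep the unadjusted chi-squared test as supportive.
- State whether randomisation was stratified by severity. If it was, add that factor to the model.
- If outcomes by arm have already been seen, leave the crude test as primary and label the adjusted analysis post hoc.

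The cost is a few lines of SAP text and a short scripted step. The logistic fit is standard in SPSS, but the standardised difference and its interval cannot be read off the coefficients. The other price is lower power in a trial where chance puts more severe women in the balloon arm: about 95% down to 91% at slope 0.3.

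### Does the SAP need an explicit analysis set and denominator for its recurrence test, given the 20% drop-out it plans for?

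*SAP*

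**What the plan says.** Section 2 of the SAP assumes recurrence of 46% with the balloon and 18% with IUD plus Foley catheter, with a type 1 error of 0.05 and a type 2 error of 0.10. It concludes that "the number of subjects required was 53 in each arm". It then allows for loss: "After assuming the drop-out rate of 20%, the total number of subjects required was 132".

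Section 3 gives the test for recurrence: "The rate of reformation adhesions were described as percentages and were evaluated using chi-squared" or Fisher's exact test, two-sided. For the adhesion score it says "The Mann-Whitney test was used to compare the reduction of AFS score between the groups". It does not name an analysis set or denominator for either comparison, or say what happens to women with no second look.

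The Protocol (Methods of investigation, Experimental procedure) fixes when the outcome is seen: "Uterine adhesions were judged again at the second hysteroscopy". One entry criterion is that women "agreed to have second-look hysteroscopy".

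**The concern.** A percentage needs a denominator, and here two are available: women who had a second look, or all women randomised with some outcome assigned to those who did not. Planned loss of one woman in five is enough for the choice to matter. The versions differ in power and can fall on opposite sides of 0.05 in the same trial.

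Return could also differ by arm. The Protocol says "Foley Catheter is removed after three days while IUD removed at the second hysteroscopy", whereas the balloon is "removed on the 7th day after surgery". Women with a device still in place have an extra reason to come back, so more loss in the balloon arm is conceivable. Neither document gives return rates.

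The SAP's date (12/01/2017) falls after the August 2016 start of recruitment on either reading of the day and month. An unstated rule could therefore have been settled with some outcomes in view. The AFS comparison has the same gap, because a reduction needs a second-look score.

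**Working it through.** **Inputs.** From SAP section 2: 46% and 18%, alpha 0.05, beta 0.10, 53 per arm, 20% drop-out, 132 in total (66 per arm). From section 3: two-sided testing. Assumed, because the documents do not say: 20% loss in each arm, unrelated to recurrence, unless stated otherwise. Results are for the uncorrected chi-squared test unless Fisher is named.

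**1. The plan's own sample size.** The unpooled formula gives

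n = (1.960 + 1.282)² × (0.46×0.54 + 0.18×0.82) / 0.28² = 10.507 × 0.396 / 0.0784 = 53.07 per arm, stated as 53.

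For loss: 106 / 0.8 = 132.5, stated as 132. In reverse, 132 × 0.8 = 105.6, about 2 × 53. The 53 per arm are therefore women with an observed outcome, and the 10% type 2 error belongs to an analysis of them.

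**2. Power under each denominator (exact binomial).** With missing women counted as recurrences, the rates become 0.8×46% + 20% = 56.8% and 0.8×18% + 20% = 34.4%. Counted as non-recurrences, they become 0.8×46% = 36.8% and 0.8×18% = 14.4%.

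| Analysis | Per arm | Rates | Chi-squared | Fisher |
|---|---|---|---|---|
| Women with a second look | 53 | 46% v 18% | 88.9% | 83.9% |
| All randomised, missing = recurrence | 66 | 56.8% v 34.4% | 72.8% | 66.8% |
| All randomised, missing = no recurrence | 66 | 36.8% v 14.4% | 85.2% | 80.5% |

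**3. How often the versions disagree (simulation, 1,000,000 trials, random 20% loss, planned rates).** Power for returners is 88.5%. Returners and missing-as-recurrence disagree on significance in 18% of trials. Returners and missing-as-no-recurrence disagree in 5.8%.

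**4. Type I error with no true difference (common rate 18%, 32% or 46%).** A fixed returners rule rejects in 5.1%. Reporting the most favourable of the three versions rejects in 8.6% to 9.3%. If loss is unequal (18 v 8 expected, an assumed split) but unrelated to recurrence, the returners test stays at 5.1%. Missing-as-recurrence then rejects in 15% to 33%, and missing-as-no-recurrence in 7% to about 13.5%.

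**5. A typical result at the planned rates, 13 missing per arm.**

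- Returners: 24/53 v 10/53, p = 0.004.
- All missing as recurrences: 37/66 v 23/66, p = 0.014.
- None as recurrences: 24/66 v 10/66, p = 0.005.

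Varying recurrences among the missing from 0 to 13 in each arm gives 14 × 14 = 196 combinations. Significance is lost in 58 (69 by Fisher). Each of the 58 needs at least 3 more recurrences among missing IUD-arm women than among missing balloon-arm women, against the planned direction.

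**6. Loss related to recurrence, same probabilities in both arms, 20% overall (assumed).** If recurrers are five times as likely to be lost (43.9% v 8.8%), the observed rates are 34.4% v 11.9%, a gap of 22.5 points instead of 28. If they are one-fifth as likely (5.4% v 26.9%), the rates are 52.4% v 22.1%, a gap of 30.3. The odds ratio is (0.46/0.54)/(0.18/0.82) = 3.88 before and after, because the loss factors cancel between arms. With no true difference, this pattern would leave the arms equal.

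**The case for a change.** The best argument for a change is that a drop-out allowance is not an analysis rule. A trial can recruit extra women and still analyse everyone randomised. Agreement to a second look at entry does not settle the matter either, since the sponsor still plans for 20% loss. With the denominator open and the SAP dated after recruitment began, the most favourable version could be reported, at a type I error of up to 9.3%. A sentence or two would name the set at almost no cost.

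Part of this stands. The text is silent, the figures reproduce, and a fuller SAP would have named the set and promised counts by arm of women randomised, seen and not seen at second look.

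The rest is weaker. The 9.3% requires choosing among three analyses after the results are known, and nothing in the documents shows that this happened. A rule added after recruitment began would not fully dispel that suspicion. The 18% disagreement depends on counting every missing woman as a recurrence, which neither document proposes. For the AFS reduction there is no such alternative, because a woman without a second look has no score to subtract. A descriptive table of possible outcomes for missing women would be useful in a report, but with no decision threshold it would not alter the test or its conclusion.

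**Conclusion.** No change to the plan follows. This is a gap that an analyst fills sensibly from the rest of the document. The sample size is built on women with an observed outcome, the outcome exists only at the second look, and comparing randomised arms as assigned is the ordinary reading. On that reading the recurrence test has about 89% power by chi-squared (about 84% by Fisher's exact test) and 5.1% type I error. Unequal loss alone does not disturb the type I error.

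Power in an all-randomised analysis ranges from about 73% to about 85%, depending on the outcome given to missing women. Both figures assume 20% loss per arm unrelated to recurrence. A typical result at the planned rates is significant under all three versions.

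The conclusion has one limit. If the link between loss and recurrence differed by arm, a returners analysis could show a spurious difference. The documents give no return rates from which to judge that, and naming a denominator would not cure it.
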